## **7. ADVERSE EVENTS AND REPORTING PROCEDURES**

### **7.1 Adverse Event**

An adverse event is any event that is presents during the trial that was not observed at baseline or has worsened from baseline.

### **7.2 Serious Adverse Event**

A serious adverse event is defined (21CFR§312.32) as any adverse experience that suggests a significant hazard, contraindication, side effect, or untoward medical occurrence that:

- Results in death,

- Is life-threatening (Note: the term “life-threatening” refers to an event in which the subject was at risk of death at the time of the event rather than to an event which hypothetically might have caused death if it were more severe),
- Requires (or prolongs) hospitalization,
- Causes persistent or significant disability/incapacity,
- Results in congenital anomalies or birth defects, or
- Other conditions which in the judgment of the Investigator represent significant hazards

Medical and scientific judgment should be exercised in deciding whether expedited reporting is appropriate in other situations, such as important medical events that may not be immediately life-threatening or result in death or hospitalization, but may jeopardize the subject, or may require intervention to prevent one of the other outcomes listed in the above definition. These should be considered serious.

Any pregnancy which occurs during this clinical trial must be reported to the Sponsor and treated as a serious adverse event with regard to the reporting time line. Any pregnancy must be followed through conclusion of the pregnancy (delivery or termination). Administration of study drug will be discontinued in a subject who becomes pregnant. If a male subject reports a pregnancy of his spouse or significant other while participating in the trial, data regarding the outcome of this pregnancy must be collected.

### **7.3 Assessment of Causality**

For any adverse event that occurs during this study, it will be the responsibility of the Investigator to assess the relationship of the event to study treatment.

For this clinical trial, the following criteria will be used:

- *Unrelated*: There is no temporal relationship between the event and the administration of the study drug, and/or the event is clearly due to the subject’s medical condition, other therapies, or accident.
- *Possibly-related*: There is some temporal relationship between the event and the administration of the study drug and the event is unlikely to be explained by the participant’s medical condition or other therapies.
- *Probably-related*: The temporal relationship between the event and the administration of the study drug is compelling, and the participant’s medical condition or other therapies cannot explain the event.
- *Definitely-related*: The temporal relationship between the event and the administration of the study drug is compelling, the participant’s medical condition or other therapies cannot explain the event and the event follows a known or suspected response pattern to the medication.

Note that for this clinical trial, adverse reactions defined by the panitumumab package insert are considered “Expected” as cited by 21CFR§312.32(a).

### **7.4 Severity of Adverse Events**

Adverse events will be graded per NCI Common Terminology Criteria for Adverse Events (CTCAE v5.0).

- Mild (Grade 1)
- Moderate (Grade 2)
- Severe (Grade 3)
- Immediately life-threatening/Fatal (Grade 4 and 5)

Adverse events that are solely laboratory test results without clinical consequence or sequelae or hospitalization will be graded by investigator judgement.

## **7.5 Safety Monitoring and Reporting**

### **7.5.1 Monitoring of Adverse Events**

Both serious and non-serious adverse events (AEs) will be clearly noted in source documentation and listed on study specific Case Report Forms (CRFs). The Protocol Director (PD) or designee will assess each AE to determine whether it is unexpected according to the Informed Consent, Protocol Document, package insert, or cross-referenced Investigator's Brochure, and related to the investigation.

All adverse events (AEs), regardless of seriousness or relationship to study drug, are to be collected only on designated study dates from signing of informed consent through 30 days after administration of study drug, and recorded in the study specific worksheets, with the following exceptions:

- AEs that are solely laboratory values; are not related to the study drug; AND are clinically non-significant may not be collected.
- Non serious AEs that are not related to the study drug; are not clinically significant; AND are expected in the post-surgery clinical setting may not be collected.
- SAEs that occur from signing of informed consent to prior to administration of study agent may not be collected unless assessed as possibly, probably or definitely-related to a study procedure.

All patients enrolled in this study receive surgical intervention in the course of their standard of care. As a consequence of this surgery, patients may experience certain expected and normal adverse events. The following post-operative adverse events will be captured only in the patient's Electronic Health Record (EHR) source documentation and not in the adverse event log. If the adverse event exceeds the grading listed below or occurs outside the post-operative time window, the adverse event will be recorded in the Adverse Event Logs.

- Surgical wound site and associated, expected secondary signs and symptoms, including:
  - CTCAE v5.0 Grade 1 erythema, edema, and pruritis.
  - CTCAE v5.0 Grade 1 pain associated with surgical wound, including headaches – mild pain, little to no limit on adult daily life.
  - CTCAE v5.0 Grade 1 nausea, vomiting, and dysphagia.
  - CTCAE v5.0 Grade 1 weight loss, anemia, and electrolyte abnormalities.
  - CTCAE v5.0 Grade 2 trismus.

Whenever possible, symptoms should be grouped as single syndrome or diagnosis. The Investigator should specify the date of onset, maximal intensity, corrective therapy given, outcome, and his/her assessment of causality.

Any AE that is not resolved by the end of the study and considered to be potentially related to study drug or was the cause for the subject's withdrawal will be followed as clinically indicated until its resolution, or if non resolving, until considered stable. All SAEs will be tracked until resolution, or until 30 after the last dose of the study treatment.

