##### **5.2.1.1.5. Digestive**

Abdominal discomfort; diarrhea; nausea; vomiting.

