##### **5.2.2.1 Dermatologic and Soft Tissue Toxicity (Black Box Warning)**

Studies reporting dermatologic toxicities have given therapeutic doses of panitumumab repeatedly during treatment cycles since this is required to achieve a tumor response. In the proposed study we give one, sub-therapeutic dose.

In one study, dermatologic toxicities occurred in 90% of subjects and were severe (NCI CTC Grade 3 and higher) in 16% of subjects (package insert). The clinical manifestations included, but were not limited to, dermatitis acneiform; pruritus; erythema; rash; skin exfoliation; paronychia; dry skin; and skin fissures. Subjects who develop dermatologic or soft tissue toxicities should be monitored for the development of inflammatory or infectious sequelae. Life threatening and fatal infectious complications including necrotizing fasciitis; abscesses; and sepsis have been observed in subjects treated with panitumumab. Panitumumab should be withheld or discontinued for toxicities associated with severe or life-threatening inflammatory or infectious complications.

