### **5.2.2.5 Hypomagnesemia and Electrolyte Abnormalities**

In one study, hypomagnesemia (NCI-CTC Grade 3 or 4) requiring oral or intravenous electrolyte repletion occurred in 2% of subjects. Hypomagnesemia occurred 6 weeks or longer after the initiation of panitumumab (package insert). Both hypomagnesemia and hypocalcemia occurred in some subjects. Electrolytes should be monitored periodically during treatment and for 8 weeks after the completion of therapy. Replete electrolytes as necessary using standard infusion guidelines.

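### The post-operative event list in Section 7.5.1 has no unrelatedness condition, so the adverse-event log can under-count related Grade 1 events after surgery

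*Combined protocol and SAP*

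**What the plan says.** Section 7.5.1 opens by placing serious and non-serious events on study case report forms (CRFs), whatever their relation to study drug, and then makes exceptions. The first covers events that are laboratory values only; they may be omitted if they are also unrelated and clinically non-significant. The second covers "Non serious AEs that are not related to the study drug; are not clinically significant; AND are expected in the post-surgery clinical setting". Both make unrelatedness a condition. The third concerns serious events before dosing and is not at issue.

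A separate paragraph then introduces a fixed list of events expected after the operation. These are recorded only in "Electronic Health Record (EHR) source documentation and not in the adverse event log". All items sit under a bullet about the surgical wound and its secondary signs. One reads "CTCAE v5.0 Grade 1 weight loss, anemia, and electrolyte abnormalities". The stated route back into the log is this condition: "If the adverse event exceeds the grading listed below or occurs outside the post-operative time window". The length of that window is not given anywhere.

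Section 5.2 names several of the same terms as toxicities:

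- Section 5.2.2.1, panitumumab skin effects: "dermatitis acneiform; pruritus; erythema; rash; skin exfoliation".
- Section 5.2.2.5, electrolytes: "Both hypomagnesemia and hypocalcemia occurred in some subjects".
- Section 5.2.1.1.5, deferoxamine: "Abdominal discomfort; diarrhea; nausea; vomiting".
- Section 5.2.1.1.3, deferoxamine systemic reactions, adds headache. Section 5.2.1.1.1, its injection-site reactions, adds pain and local edema.

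**The concern.** Two rules in one section can treat the same event differently. A Grade 1 electrolyte change after surgery that might be drug-related cannot be omitted under the laboratory exception, which needs it to be unrelated. Under the fixed list it stays out of the log. The same holds for Grade 1 nausea under the post-surgery exception and the list.

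The log matters even though Section 12 specifies no safety table. The synopsis says safety data and adverse events will be reported 15 days after the last infusion, Section 4.3 picks Day 15 as the safety time point, and Section 7.5.2 sends non-serious events to the FDA and IRB yearly. Section 2.4 describes the study chemistries, including magnesium and phosphorus, as a means of finding acute and late toxicity, so the list can remove Grade 1 results of a test done for that purpose. Section 2.3 describes the study as the first in humans to combine these two agents for this use. With 14 subjects, the causality of a mild event should be recorded, not settled in advance by its name.

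**Working it through.** This is mainly a check of text against text; the plan states no adverse-event rate to reproduce.

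**1. Conditions for leaving an event out of the log (all Section 7.5.1)**

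| Rule | Must be unrelated? | Other conditions |
|---|---|---|
| Laboratory-only exception | Yes | Clinically non-significant |
| Post-surgery exception | Yes | Non-serious, not clinically significant, expected after surgery |
| Fixed list | Not stated | Listed term, at or below the listed grade, inside an undefined window, introduced as a result of surgery |

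**2. Overlap with Section 5.2.** The list has 12 terms: erythema, edema, pruritus, pain, headache, nausea, vomiting, dysphagia, weight loss, anemia, electrolyte abnormalities and trismus. Eight also appear as toxicities: erythema, edema, pruritus, pain, headache, nausea, vomiting and electrolyte abnormalities. For edema and pain the match is weak, since Section 5.2 has them as injection-site reactions and the list's pain is wound pain. Dysphagia, weight loss, anemia and trismus are not named as toxicities. All eight overlapping terms are listed at Grade 1; the only Grade 2 item is trismus.

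**3. Timing.** Surgery is on Day 2 to 5. After the day of surgery, Table 5 schedules chemistries only on Day 15. That visit falls 15 − 5 = 10 to 15 − 2 = 13 days after surgery. With the ±4-day visit window the range is 11 − 5 = 6 to 19 − 2 = 17 days. Whether a Grade 1 result at that visit is logged depends on the undefined window.

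**4. Stopping rule.** Section 4.4 starts dose-limiting toxicity (DLT) at Grade 2, so the eight Grade 1 terms cannot alter it. The plan's only safety probability is in Section 2.4, the chance of two or more DLTs among 10 subjects, and it reproduces:

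- 1% rate: 1 − 0.99^10 − 10 × 0.01 × 0.99^9 = 0.0043 (stated 0.4%)
- 5% rate: 1 − 0.95^10 − 10 × 0.05 × 0.95^9 = 0.0861 (stated 8.6%)

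Neither figure depends on the list.

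**5. Size.** One missed subject is 1/14 = 7.1 percentage points. Beyond that, both inputs must be assumed: r, the share of subjects with a related Grade 1 listed event, and q, the share of those sent to the health record only. Expected subjects logged = 14 × r × (1 − q).

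| Assumed r | True expected (14r) | Logged, q = 0 | q = 0.5 | q = 1 |
|---|---|---|---|---|
| 10% | 1.4 | 1.4 | 0.7 | 0 |
| 30% | 4.2 | 4.2 | 2.1 | 0 |

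At r = 10%, the chance that the log shows at least one such subject is 1 − 0.9^14 = 0.771 when q = 0 and 1 − 0.95^14 = 0.512 when q = 0.5. These figures illustrate the mechanism and do not estimate what will happen.

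**The case against.** The best defence is that the list is not applied by term and time alone. It is introduced as a result of the operation and sits under a bullet about the wound. Headache appears only with wound pain, and a rash away from the wound hardly fits. Section 7.3 also requires a causality assessment for every event, and its definition of possibly-related excludes events that other therapies readily explain. An event truly attributed to surgery would seldom be called possibly related.

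Much of this stands, and it narrows the problem. It does not close it. Nausea, vomiting and electrolyte changes have no location that separates drug from surgery. The section does not say that the Section 7.3 assessment comes before the list is applied, and being judged related is not among the stated routes back into the log.

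Several mitigating points also stand. Section 7.5.2 has abnormal laboratory and clinical assessments, and symptoms that subjects report, captured in the CRF, so part of the information reaches the study data. Section 5.2.2.5 places hypomagnesemia at six weeks or later, and Section 5.2.2.1 ties the skin effects to repeated therapeutic doses. Section 5.2.2 expects mainly infusion or allergic reactions; reactions on Day 0 precede surgery and would still be logged.

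A reader might infer that most of follow-up is lost, since (30 − 5)/30 = 83% to (30 − 2)/30 = 93% of the 30 days come after surgery. The documents do not support that. The window is undefined, and events are collected only on designated dates, so calendar days do not measure what is observed.

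**Conclusion.** The point holds as a limited one. As written, the log can under-count related Grade 1 events after surgery, chiefly nausea, vomiting and electrolyte changes, because the list lacks the unrelatedness condition that the neighbouring exceptions carry. This rests on reading the list paragraph as a free-standing rule, which its wording supports.

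It would go too far to say that drug effects will be under-counted in a safety table. No such table is defined, no rate is given, and the text shows only that events can be missed. Each missed subject is worth 7.1 points; the total is unknown. The DLT rule is not affected by the overlapping terms, pre-surgery events are logged, and the source data can be recovered. Nor do the documents support a rule that every electrolyte change must be logged, since that would contradict the laboratory exception in the same section.

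**What to change.** Add one sentence to the list paragraph in Section 7.5.1: the list applies only to events assessed as Unrelated under Section 7.3, with onset after surgery and within a stated number of days of it. The sponsor should supply that number. In the same edit, reconcile the list with the laboratory and post-surgery exceptions and with the opening CRF sentence, so that one event has one route.

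The cost is a short amendment and a few more log lines of mild events, each carrying a causality assessment that Section 7.3 already requires.

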### **7.5.2 Recording and Reporting Adverse Events and Serious Adverse Events**

Non-serious adverse events will be reported annually to the FDA via an Annual Report and to the IRB via Continuing Review.

The PD (aka Principle Investigator) must immediately report within 24 hours of knowledge of event to the Sponsor-Investigator (i.e. IND Holder, [name], MD), any serious adverse event, whether or not considered related to study drug. SAEs of all grades will be reported to the Sponsor-Investigator using the Stanford Cancer Institute SAE CRF. The investigator must provide a detailed description of the event, the treatment regimen, relevant laboratory and evaluations and assessment of the relationship of the AE to the study drug. All relevant information should be reported as it becomes available.

SAEs CTCAE Grade 3 and above, and all subsequent follow up reports will be reported to the Stanford Cancer Institute Data and Safety Monitoring Committee (DSMC) using the study specific CRF regardless of the event's relatedness to the investigation. Following review by the DSMC, events meeting the IRB definition of 'Unanticipated Problem' will be reported to the IRB using eProtocol within 10 working days of DSMC review, or within 5 working days for deaths or life threatening experiences.

Adverse events deemed serious, unexpected (i.e. not described in the protocol, package insert, cross-referenced Investigator's Brochure or informed consent documents) and related to study drug must be reported to Sponsor-Investigator using the FDA MedWatch form 3500a within 24 hours of knowledge of event. The Sponsor Investigator is responsible for deciding whether the event meets IND Safety Reporting criteria.

Events will be submitted to Sponsor Investigator [name], MD, at:

-----  
[name], MD, Professor of Radiology  
Dept of Radiology, Division of Nuclear Medicine  
Stanford Medicine at Stanford University M/C 5281  
[name]  
[name]  
[REDACTED]  
[REDACTED]

It will be the responsibility of the Sponsor-Investigator to provide to the FDA all information concerning significant hazards, contraindications, side effects or precautions felt significant to the safety of the drug being studied. The PD is responsible for accurate and timely communication to the Sponsor-Investigator of any events reportable to FDA. Subjects will be instructed prior to participation on the importance of reporting any symptoms (new or worsening), and/or any physical changes throughout their participation in the study. These events will be recorded accordingly in the CRF. Abnormal laboratory and/or clinical assessments will also be captured in the appropriate CRF.

## **8. CORRELATIVE/SPECIAL STUDIES**

Conform our phase I study (IRB-35064), we will continue collecting pharmacokinetics data, hence the blood draws. We will also continue collecting imaging data on the primary tumor. This data will be used for: 1) drug delivery studies to gain better insight in the panitumumab-Irdye800 distribution in the tumor; and 2) to further study if the drug can be used to define (intraoperative) margins. Furthermore preoperative standard of care imaging obtained during routine evaluation will be used to correlate with pathological findings.

## **9. STUDY CALENDAR**

### **9.1 Study Procedures**

Enrolled subjects will follow the schedule of evaluations provided below.

**Table 5: Study Procedures**

	SCREENING/ PRE-TREATMENT (WITHIN 30 DAYS OF START OF TREATMENT)	DAY 0	DAY 1-4	DAY OF SURGERY (DAY 2 TO 5)	DAY 15 ( $\pm$ 4 days)	DAY 30 ( $\pm$ 4 days)
INFORMED CONSENT	X					
MEDICAL HISTORY	X					
PHYSICAL EXAMINATION 	X	X			X	
VITAL SIGNS	X	X		X	X	
HEIGHT AND WEIGHT	X					
PERFORMANCE STATUS 	X				X	
ECG	X 	X 			X	
CHEMISTRIES 	X	X		X	X	
HEMATOLOGY 	X				X	
TSH	X					
PTT/PT/INR	X					
SERUM PREGNANCY 	X	X				
PK-FLUORESCENT-LABELED ANTIBODY 		X	X	X	X	
PK-IMMUNOGENICITY 		X 			X	
IV INFUSION OF PANITUMUMAB-IRDYE800 		X				
BOLUS INJECTION OF  ZR-PANITUMUMAB 		X				
SURGICAL RESECTION 				X		
TUMOR IMAGING	X 	X 	X 	X 		
PATHOLOGICAL EVALUATIONS 				X		
ADVERSE EVENTS 		X		X	X	X
CONCURRENT MEDICATIONS 	X	X	X	X	X	X

1. A physical examination will be done at baseline; standard head and neck examination and system-oriented physical examination will be conducted on Day 0 and Day 15. Examinations do not have to be repeated on Day 0 if completed within 21 days prior to infusion. Performance status assessment will be done at baseline and Day 15. Examinations collected for surgical procedure are acceptable for screening purposes.
2. An ECG will be obtained at screening to evaluate baseline. A previous ECG that was obtained as part of standard of care may be used as the baseline ECG if obtained within 21 days prior to infusion.
3. On day of infusion, ECG will be collected 30 ( $\pm$ 10) min after the end of panitumumab-IRDye800 infusion. Also an ECG will be obtained at the end of the 1 hour ( $\pm$ 10 mins) observation period after completion of injection of Zr-panitumumab.

4. Chemistries to include a standard basic metabolic profile with magnesium and phosphorus. Chemistries and other blood work collected for surgical procedure are acceptable for screening purposes. Chemistries do not have to be repeated on Day 0 if completed within 21 days prior to infusion.
5. Hematology (i.e., CBC) values include WBC; RBC; Hgb; hematocrit and platelet counts. Blood work collected for surgical procedure are acceptable for screening purposes.
6. A serum pregnancy test will be obtained on all women of childbearing age at baseline; a urine pregnancy test will be performed on Day 0 if the result of a serum pregnancy test within 72 hours before administration of panitumumab-IRDye800 is not available.
7. Blood samples for serum level of panitumumab-IRDye800 antibody and unconjugated dye, and  $^{89}\text{Zr}$ -panitumumab antibody will be drawn as follows: on Day 0 prior to panitumumab-IRDye800 infusion and at the end of the 1-hour ( $\pm 10$  mins) observation period after completion of injection of  $^{89}\text{Zr}$ -panitumumab; on Day 1-4 (only one sample will be collected on the same day when the PET/CT will be performed); on Day of surgery and on Day 15. The Day 15 time point will be 15 days  $\pm$  4 days, but is abbreviated as Day 15 throughout the protocol.
8. Blood will be collected on Day 0 prior to panitumumab-IRDye800 dose and on Day 15 and banked for future immunogenicity testing. Immunogenicity testing time points will not vary with dose.
9. Panitumumab-IRDye800 infusion to be given over 15 ( $\pm 5$  mins) minutes followed by 30 minutes ( $\pm 10$  mins) observation period.
10.  $^{89}\text{Zr}$ -panitumumab administered as a bolus injection to be done after the end of the observation period after panitumumab-IRDye800 infusion; will be followed by 1 hour ( $\pm 10$  mins) of observation period.
11. Surgical excision will be performed 2-5 days after the infusion of the study drugs.
12. A  $^{89}\text{Zr}$ -PET/CT scan will be acquired after injection of  $^{89}\text{Zr}$ -panitumumab. One scan will be performed at any time starting on Day 0 (after end of observation period post  $^{89}\text{Zr}$ -panitumumab administration) and until the day before surgery (inclusive). Subjects enrolled in the dosimetry sub-study will undergo three scans, performed at any time starting on Day 0 (after end of observation period post  $^{89}\text{Zr}$ -panitumumab administration) and until the day before surgery (inclusive); if available, the scans will be performed on Day 0, Day 1 and on the day before surgery.
13. A standard of care  $^{18}\text{F}$ -FDG-PET scan acquired within year from the day of study drug infusion is acceptable, even if this scan was/is acquired outside of Stanford.
14. Radiotracing and fluorescence imaging: Lymph node (and primary tumor) imaging will be done using the optical imaging devices (see Appendix B), in the clinic on Day 0 and at any other clinic visits between infusion and surgery if tumor is amenable to imaging and depending on subject availability. Radiotracer detection using the devices listed in Appendix C will be performed during surgery. Lymph nodes (and primary tumors) will be imaged intraoperatively to determine threshold of detection. Following surgery, pathological assessment of the specimens will take place.
15. See Section 7.5.1 for adverse events monitoring and reporting.
16. Concurrent medications will be recorded at screening. Medications administered on the Day 0 until Day 30 will not be collected unless given for a reportable adverse event or reportable serious adverse event.

